#### **D.2.g. Program Completion**

Participants will receive an order to complete the HbA1c at 12 and 24 weeks at any OSU lab. A reminder letter will be sent 1 week prior to the date and a phone call reminder will occur 2 days before the visit. Study team will complete the 12 week and 24 week call and search the electronic medical record and primary provider's chart for HbA1c and healthcare utilization at 12 and 24 weeks.

**E. Study Drug:** Patients in both groups will be provided standard of care insulin therapy throughout the study, including insulin glargine (TOUJEO® U300) plus additional background therapy (non-insulin and prandial insulin therapies), based upon discharge team preference. The starting dose will be determined during hospitalization from the dose of glargine/detemir U100 in a 1:1 dose conversion. Upon discharge, standard titration instructions (every 4 days) will be implemented in the DOS group but will be left to the discretion of the discharge team in the ESC group.

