#### **F.1.b. Follow-up Encounters**

Study staff will conduct phone calls or email communications at 2 and 6 weeks to confirm contact information and inquire about discharge follow-up. Patients will be given an appointment day and time prior to discharge for the first phone contact at 2 weeks. Any specific medical concerns reported during any call will be forwarded to the primary provider. At 12 and 24 weeks, HbA1c is measured and the staff will assess outpatient follow-up, hospital readmission or emergency department visit, adherence to insulin and glucose monitoring, hyperglycemic and hypoglycemic events, and perform the DES-SF.

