#### H.1.a. Missing Data

All data analyses will be completed as intention to treat analyses (i.e., individuals analyzed by group according to original random assignment, without regard to adherence to the intervention).

Longitudinal outcomes (e.g., HbA1c) will be analyzed using mixed models utilizing all available measurements from individuals randomized. Missing binary outcomes (e.g., accurate and complete discharge orders, adherence) and missing covariate data will be imputed, using multiple imputation in SAS v9.3 PROC MI.

Table 9. Study Procedures and Visits

Visit number	0	1	2	3	4
Time of Visit	Screen/consent	2 week	6 week	12 week	24 week
Type of visit	In-person	Phone	Phone	In-person	In-person
Informed consent/contact team	x				
Randomization	x				
Load DOS into EMR and inform discharge team	x				
Provide study drug and glucose monitoring instructions	x				
Demographics/Socioeconomic status	x				
Diabetes history	x				
Hospitalization history	x				
PSS scale	x				
DES-SF	x			x	x
Newest Vital Sign	x				
Glucose/insulin diary	x				
Review DOS		x			
Ascertain health care utilization		x	x	x	x
Review glucose/insulin diary		x	x	x	x
Hypoglycemia/Hyperglycemia		x	x	x	x
Review insulin adherence, persistence		x	x	x	x
Nurse counsellor (DOS group only)		x	x	x	x
HbA1c	x			x	x
Fasting blood glucose	x			x	x

DOS=discharge order set, EMR=electronic medical record, PSS=Perceived Social Support scale, DES-SF=Diabetes empowerment scale-short form, In-Person clinic visits will be conducted at either CarPoint East or McCampbell Hall

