### H.2.a. Statistical Power and Sample Size

The sample size for our study was based on a comparison of change in HbA1c over three months adjusting for baseline covariates related to change in HbA1c: age, whether or not patient is new to insulin, and dose of insulin; the first two were selected based on our preliminary data and the latter was selected based on an expected relationship. The following expression, adapted from Oakes and Feldman, was used to calculate the number of individuals per group:

$$n/group = \frac{4\sigma^2(1-\rho)(1-R^2)(Z_{1-\alpha/2} + Z_{1-\beta})^2}{\Delta^2}$$

where  $\sigma$  is the standard deviation of HbA1c,  $\rho$  is the correlation between baseline and 24 week HbA1c levels,  $R^2$  is the proportion of variability in change in HbA1c explained by the baseline covariates,  $\Delta$  is the difference in change in HbA1c between treatment groups, and  $Z_{1-\alpha/2}$  and  $Z_{1-\beta}$  are standard normal quantiles calculated at the two-sided type-I error rate ( $\alpha$ ) and power (1- $\beta$ ). Using parameter values based on our preliminary data ( $\sigma = 2.2\%$ ,  $\rho = 0.25$ ,  $R^2 = 0.5$ ) and based on the effect observed by Wexler ( $\Delta = 0.8\%$ ), we will need 89 individuals per treatment group with 24 week follow-up to achieve 80% power at  $\alpha = 0.05$ . Since we expect 20% attrition, we will recruit 111 individuals per group into our study. The study is powered to detect a difference in the primary endpoint only. However, additional secondary endpoints of strong interest are pre-specified and included in the analysis.

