**Secondary:**

- Difference in the change in HbA1c from baseline to 12 weeks (+/-2 weeks) post-discharge (%, mmol/l)
- Difference in the change in HbA1c from baseline to 12 and 24 weeks (+/-2 weeks) post-discharge (%, mmol/l)
- Difference in the change in fasting plasma glucose (FPG) from baseline to 12 and 24 weeks in DOS vs ESC (mg/dl)
- Difference in the % of patients achieving HbA1C 7% in DOS vs ESC (12, 24 weeks)
- Difference in the % of patients achieving HbA1C 6.5% in DOS vs ESC (12, 24 weeks)
- Difference in the % of patients achieving individualized HbA1C target in DOS vs ESC (12, 24 weeks)
- Difference in the proportion of patients with accurate and complete discharge orders for basal insulin and related supplies. (%)
  - Assessed as complete dose, quantity dispensed, adequate refills (separate for basal and prandial insulin), and correct prescription for pen needles (presence, quantity, adequate refills), no jargon
- Difference in the proportion of patients with accurate and complete discharge orders for prandial insulin and related supplies. (%)
  - Assessed as complete dose, clear dosing instructions, quantity dispensed, adequate refills, and correct prescription for pen needles (presence, quantity, adequate refills), no jargon
- Difference in the proportion of patients with a discharge prescription for glucose monitoring supplies (%)
- Difference in adherence to glargine U300 (% taking >80% of doses) at 2, and 24 weeks
- Difference in the proportion of patients who remain on glargine U300 at 24 weeks (%)
- Difference in the mean dose of glargine U300 at 2 and 24 weeks (units)
- Difference in the frequency of glucose monitoring at 2 and 24 weeks (times per day)
- Difference in the proportion of patients who follow up with their primary care provider or endocrinologist within 2, 6 weeks of discharge (%)
- Difference in the incidence of documented symptomatic (BG <54 mg/dl) hypoglycemia (%)

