**H.2.c Primary Aim: To determine whether a Discharge order set with nursing support (DOS) is associated with lower HbA1c at 24 weeks post-program than enhanced standard care (ESC) alone.** We will test for a difference in 24 week change in HbA1c between the DOS and ESC groups using a linear mixed model for the longitudinal HbA1c measurements. Our model will contain a random subject-specific effect and fixed effects of time (baseline vs. 24 weeks), treatment, a treatment-by-time interaction, and baseline covariates related to change, which we expect to include age, whether or not patient is new to insulin, and dose of insulin based on our preliminary data. We will adjust for changes in prandial insulin dose by including dose as a time-varying covariate in our mixed models. The inclusion of covariates is not to account for differences in these factors across treatment groups (which we don't expect due to randomization) but to increase the precision of our treatment effect estimate. A Wald test of the treatment-by-time interaction will be used to test our primary hypothesis that DOS affects 24 weeks change in Hb1Ac.

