#### H.2.d. Secondary Aims:

- Determine whether DOS is associated with lower HbA1c at 12 months compared to ESC.
- Determine whether the DOS in conjunction with nurse supported self-titration of basal insulin glargine U300 is associated with improved persistence with insulin therapy, adequate dose titration, and use of self-monitored blood glucose.
- Determine whether the DOS is associated with improved discharge instructions and processes of care for insulin-requiring patients. This will be measured in terms of clarity of instructions, adequacy and completeness of prescriptions for insulin and diabetes supplies, and follow-up plan.

Each of these secondary outcomes will be binary (e.g., adequate vs. inadequate dose titration). Missing values of the outcomes will be imputed using treatment group and baseline covariates. The difference in proportions between treatment groups will be computed for each data set and the results will be combined using Rubin's rules to obtain a final two-sample test of proportions.

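### The primary HbA1c model leaves out the week-12 value that H.1.a promises to use; if later dropout tracks week-12 control differently by arm, the 24-week difference is biased

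*Combined protocol and SAP*

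**What the plan says.** - **H.1.a Missing Data:** "Longitudinal outcomes (e.g., HbA1c) will be analyzed using mixed models utilizing all available measurements from individuals randomized". The same section plans multiple imputation for missing binary outcomes and covariates.
- **H.2.c Primary Aim:** the only specification of the primary test. The mixed model has a random subject effect, "fixed effects of time (baseline vs. 24 weeks" being the two levels of time, treatment, their interaction, and baseline covariates. A Wald test of the interaction is the primary test.
- **F.1.b, F.2.c and Table 9:** the week-12 value is collected in both arms. "At 12 and 24 weeks, HbA1c is measured and the staff will assess outpatient follow-up" is the F.1.b wording.
- **H.2.d Secondary Aims:** "Missing values of the outcomes will be imputed using treatment group and baseline covariates". The section does not name the HbA1c-target endpoints. H.2.b lists them as binary outcomes at both visits ("Difference in the % of patients achieving HbA1C 7% in DOS vs ESC (12, 24 weeks"), so they come under this rule through H.1.a.
- **H.2.a:** "Since we expect 20% attrition, we will recruit 111 individuals per group into our study". The timing of the loss and its split by arm are not given.
- **D.2.g:** "Study team will complete the 12 week and 24 week call and search the electronic medical record", and the primary provider's chart, for HbA1c. This may recover some values but does not alter the model.

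**The concern.** Under the H.2.c model, a patient who has a week-12 HbA1c but no 24-week value contributes only the baseline value. The model then in effect predicts the missing value from baseline, which the plan takes to correlate only 0.25 with week 24. The closest earlier measurement is ignored.

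That is harmless unless dropout after week 12 depends on week-12 HbA1c beyond arm, baseline HbA1c and covariates. If poorly controlled patients leave mainly from enhanced standard care (ESC), the remaining ESC patients look better than the arm really is and the difference shrinks. If they leave mainly from the discharge order set (DOS) arm, the difference is exaggerated. The two arms receive different post-discharge contact (nurse calls to confirm titration versus coordinator calls for data, Table 7) and the trial is unblinded in practice, so a different dropout pattern is possible.

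Separately, two analysts could fit different primary models and each claim to follow the plan.

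**Working it through.** **The plan's own figure.** The H.2.a formula with SD 2.2, correlation 0.25, R² 0.5 and difference 0.8 gives 4 × 4.84 × 0.75 × 0.5 × (1.960 + 0.842)² / 0.64 = 89.04 per group (89 stated). Then 89/0.8 = 111.25 (111 stated). The implied standard error is √(7.26/89) = 0.286. The sample size is not in question here.

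**Assumptions not in the documents.** Baseline-to-week-12 correlation 0.30; week 12-24 correlation 0.5, 0.7 or 0.8; the same effect at week 12 as at week 24; log-odds of dropout 1 per SD of week-12 HbA1c where selection acts; all loss after week 12 unless stated.

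**Check by hand, selection in one arm.** With a logistic slope of 1 and 20% lost, dropouts average 0.693 SD above the arm's week-12 mean. Completers therefore average 0.693 × 0.2/0.8 = 0.173 SD below it. Allowing for what baseline explains, the completers' 24-week mean is off by about 2.2 × 0.173 × (r − 0.25 × 0.30), where r is the week 12-24 correlation:

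- r = 0.5: 0.16
- r = 0.7: 0.24
- r = 0.8: 0.28

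ESC-only selection should then give about -0.64/-0.56/-0.52 and DOS-only about -0.96/-1.04/-1.08.

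**Simulation, maximum-likelihood mixed models** (true difference -0.80; Monte Carlo error about 0.01; columns are r):

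| Model and dropout | 0.5 | 0.7 | 0.8 |
|---|---|---|---|
| Two visits, random dropout | -0.79 | -0.79 | -0.80 |
| Two visits, same rule in both arms | -0.75 | -0.74 | -0.73 |
| Two visits, ESC-only | -0.64 | -0.55 | -0.52 |
| Two visits, DOS-only | -0.96 | -1.04 | -1.07 |
| Two visits, covariate as main effect, ESC-only | -0.62 | -0.54 | -0.52 |
| Two visits, covariate acting on change, ESC-only | -0.75 | -0.69 | -0.65 |
| Two visits, covariate acting on change, DOS-only | -0.86 | -0.92 | -0.96 |
| Half the loss random before week 12, ESC-only | -0.70 | -0.66 | -0.64 |
| The same, covariate acting on change | -0.77 | -0.74 | -0.71 |
| Three visits, random intercept only, ESC-only | -0.74 | -0.67 | -0.64 |

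Rows without a stated covariate have none; the covariate has R² = 0.5. Three visits with unstructured covariance give -0.79 to -0.81 throughout, as expected when dropout is generated from week-12 HbA1c. The same-rule row is off because one rule on absolute HbA1c removes fewer patients from the lower-HbA1c arm. If each arm loses exactly 20% under the same slope, the bias is about zero.

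**Milder inputs.** Take log-odds of ±0.7, baseline-to-week-12 correlation 0.25 to 0.5, week 12-24 correlation 0.25 to 0.7, and 10% or 20% lost after week 12. Where the relation differs by arm (DOS-only, or opposite directions), the two-visit bias runs from -0.03 to -0.33, that is 0.028/0.8 = 3.5% to 0.328/0.8 = 41% of the effect. Adding week 12 with only a random intercept leaves about 0 to -0.12; unstructured covariance leaves about 0.

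**Trial level** (1,500 trials of 111 per arm, r = 0.7, covariate acting on change), two visits versus three visits unstructured:

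- Power, ESC-only: 69% versus 84%.
- Power, random dropout: 84% versus 85%.
- Type I error, ESC-only: 7.4% versus 4.2%.
- Type I error, DOS-only: 7.1% versus 5.1%.
- Standard error: 0.279 versus 0.273.

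**HbA1c below 7% at 24 weeks** (assumed ESC mean 8.9%, true difference about 11.5 points). Imputing from arm and baseline HbA1c alone is 1.8 to 2.7 points too small under ESC-only and 2.4 to 3.9 too large under DOS-only. With an R² = 0.5 covariate in the imputation the errors are 0.4 to 1.4 and 0.7 to 1.9. With week 12 included they are within 0.1 point.

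**The case against.** The conflict can be read more softly. The H.1.a promise may mean only that patients with a baseline but no 24-week value are kept, which a two-visit mixed model does. The parenthesis in H.2.c may name the tested contrast rather than the levels of the factor. Neither section says so, and the two readings lead to different primary analyses, so the text still needs reconciling.

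The one-arm-only scenarios are extreme: an odds ratio of 2.7 per SD in one arm and none in the other. With log-odds of 1.0 in ESC and 0.5 in DOS, the two-visit estimate is about -0.73/-0.69/-0.68 without covariates and -0.79/-0.75/-0.74 with a covariate acting on change. With 0.7 and 0.35 and half the loss early, it is -0.77/-0.75/-0.74 and -0.79/-0.79/-0.77. These biases, 0.01 to 0.12, are under half of a standard error of about 0.28. This stands, and it limits how strongly the size can be put.

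The planned model does have covariates, and H.2.a defines R² in terms of change, which favours the smaller figures. However, H.2.c lists no covariate-by-time term, and as main effects covariates leave the bias nearly unchanged. The time-varying prandial dose in H.2.c was not simulated, and power under DOS-only selection was not computed.

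H.2 plans a descriptive look at differential attrition, and section I expects easier access to 24-week data for patients followed in the health system. Both help, but neither corrects the estimate. The link to H.2.d is inferred through H.1.a and concerns endpoints on which the trial is not powered.

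**Conclusion.** The concern holds. As written, H.1.a and H.2.c do not agree, and the collected week-12 HbA1c has no place in the primary test. That rests on the text alone.

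The bias is conditional. It is about zero under random dropout, small under a shared rule, and in either direction when the relation to week-12 HbA1c differs by arm: roughly 0.01 to 0.12 for graded selection, and up to about 0.28 for strong selection in one arm without covariates. The correlations, dropout slopes and timing are assumptions, and the documents give no evidence for or against arm-differential dropout. The gain in precision alone is trivial. Using week 12 does not correct loss before week 12 or loss driven by later events. The change should be made because it removes an avoidable source of bias and an ambiguity in the primary analysis.

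**What to change.** - **H.2.c:** make time a three-level factor (baseline, 12 and 24 weeks) with unstructured covariance. Keep the week-24 treatment-by-time contrast as the single primary Wald test. The same model gives the 12-week secondary contrast. State the covariance explicitly, because a random intercept alone can leave bias.
- **H.1.a:** align the wording with H.2.c.
- **H.2.d:** state that the 24-week HbA1c-target outcomes are covered, and add week-12 HbA1c to their imputation model. Discharge-order outcomes need no change.

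**Cost:** SAP wording, slightly more programming, and four more covariance parameters (six instead of two). Data collection, sample size, endpoint and alpha are unchanged.

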**Table 4. Multivariable Predictors of Change in HbA1c**

Model 1	Estimate	SE	P value
Original Model			
Intercept	25.3	5.4	<0.0001
Age	-0.086	0.028	0.004
T2DM	-0.43	0.35	0.23
Log(HbA1c baseline)	-9.82	2.00	<0.0001
New to basal insulin	-1.17	0.32	0.0008
Final Model			
Intercept	24.7	5.3	<0.0001
Age	-0.087	0.026	0.002
Log(HbA1c baseline)	-9.61	2.00	<0.0001
New to basal insulin	-1.10	0.32	0.002
Model 2	Estimate	SE	P value
Final Model			
Intercept	22.5	5.19	0.0001
Age	-0.081	0.025	0.003
First education day of discharge	0.59	0.29	0.047
Log(HbA1c baseline)	-8.86	1.95	<.0001
New to basal insulin	1.03	0.31	0.002

Abbreviations: HbA1c, glycated hemoglobin; T2DM, type 2 diabetes mellitus

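### The primary mixed model tests a change-score contrast that does not adjust for baseline HbA1c; it is valid but gives up precision that can be recovered at no cost

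*Combined protocol and SAP*

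**What the plan says.** Section H.2.c fits a linear mixed model with a random subject effect and "fixed effects of time (baseline vs. 24 weeks), treatment, a treatment-by-time interaction, and baseline covariates related to change". Baseline HbA1c enters as the first of the two outcome values. The decision rule is: "A Wald test of the treatment-by-time interaction will be used to test our primary hypothesis".

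Of the baseline covariates, H.2.c writes: "which we expect to include age, whether or not patient is new to insulin, and dose of insulin based on our preliminary data". The same three underlie the sample size in H.2.a: "age, whether or not patient is new to insulin, and dose of insulin; the first two were selected based on our preliminary data". Baseline HbA1c is in neither list. H.2.c explains that covariates are there for precision, since randomisation takes care of balance.

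H.2.a sizes the trial with the variance of a change score, 4σ²(1−ρ), multiplied by (1−R²). It uses σ = 2.2%, ρ = 0.25 between baseline and 24 weeks, R² = 0.5, Δ = 0.8% and a two-sided α of 0.05. This gives 89 per group with follow-up and 111 recruited after 20% attrition. The primary endpoint in H.2.b is the difference between arms in change in HbA1c.

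In Table 4 (section C.2.b), the log of baseline HbA1c is in all three multivariable models of change, with estimates −9.82, −9.61 and −8.86 and p<0.0001 each time.

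**The concern.** Baseline HbA1c is measured before randomisation, so the true arm means at baseline are equal and a treatment main effect can only fit chance imbalance. Once it is in the model, the interaction subtracts each arm's observed baseline mean in full. That is efficient only when baseline predicts follow-up almost one for one. The plan assumes a correlation of 0.25, so subtracting the whole baseline adds more noise than it removes.

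The plan adds covariates for precision and selects them from its preliminary data, yet the predictor with the largest t-ratio there (−9.61/2.00 = −4.8) is not used for adjustment. At stake is the precision of the only endpoint for which the trial is powered.

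**Working it through.** **Inputs.** From H.2.a: σ = 2.2 (one value for both times), ρ = 0.25, R² = 0.5, Δ = 0.8, 89 per arm with follow-up, 111 recruited. For two-sided 5% and 80% power, (1.960 + 0.842)² = 7.849.

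**1. The plan's own figure.** 4 × 2.2² × 0.75 × 0.5 × 7.849 / 0.8² = 89.04, which matches 89 (power at 89 is 79.98%). 89/0.8 = 111.25, which matches 111.

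**2. What the model tests.** A random-intercept model with treatment, time and their interaction was fitted to simulated complete pairs. The interaction equalled the difference in mean change exactly (−0.2043 both ways).
- Adding a time-invariant covariate as a main effect changed neither the estimate nor the SE (0.3926 with and without it).
- Adding baseline HbA1c as a further main effect also left the estimate at −0.2043. The model's printed SE fell to 0.294, but an identical estimate has an identical sampling variance, so that fall is not a real gain.

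The planned time-varying prandial dose is a separate matter and was left out of this check.

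**3. Variance per patient, no other covariates.**
- Change score: 2σ²(1−ρ) = 2 × 4.84 × 0.75 = 7.26.
- Baseline-adjusted: σ²(1−ρ²) = 4.84 × 0.9375 = 4.54.
- Ratio: (1+ρ)/2 = 0.625, a reduction of 37.5%.

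**4. SE and power at 89 per arm, no other covariates.**
- Change score: √(2 × 7.26/89) = 0.404; power 50.8%.
- Baseline-adjusted: √(2 × 4.5375/89) = 0.319; power 70.7%.
- For 80% power: 179 against 112 per arm, rounded up.

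**5. Sensitivity of the 37.5%.**
- *Attrition.* With 111 randomised and 89 followed per arm, and dropouts' baselines kept as H.1.a implies, the variances in units of σ² are 0.9375/89 + 0.75²/111 = 0.01560 (free baseline means) and 0.9375/89 = 0.01053 (common baseline mean). The reduction is 32.5%, and power is 54% against 71%.
- *Correlation.* The reduction is (1−ρ)/2, so 25% at an assumed ρ of 0.5.
- *Baseline SD.* Table 2 gives a type 2 baseline interquartile range of 10.1–12.6. Under normality the SD is 2.5/1.349 = 1.85. With a 24-week SD of 2.2, Var(change) = 4.84 + 3.43 − 2 × 0.25 × 2.2 × 1.85 = 6.24, and 1 − 4.54/6.24 = 27%. If the 24-week SD is instead solved from Table 2's type 2 change SD of 2.72, it is about 2.51; then 1 − (2.51² × 0.9375)/2.72² = 20%.

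**6. Link to the plan's R².** With baseline adjustment, n per arm = 2 × 4.84 × 0.9375 × 7.849/0.64 × (1−R²) = 111.3 × (1−R²), where R² is now the share explained beyond baseline HbA1c. Values of 0, 0.10, 0.20 and 0.30 give 111.3, 100.2, 89.0 and 77.9. The planned 89 therefore needs about 0.20. Since 1 − 0.625 × 0.80 = 0.50, that is the same total as the plan's R² of 0.5.

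**The case against.** The strongest reply is that this is an efficiency choice, made consistently. Endpoint, sample-size formula and test all concern change, the contrast is unbiased under randomisation, and simulation put type I error at about 5% for either analysis. All of this stands.

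The second reply is that 51% against 71% sets aside the plan's R² of 0.5, with which H.2.a reaches 80%. That also stands. The R² is said to come from preliminary data, and every multivariable model in Table 4 contains baseline HbA1c, while H.2.a names other covariates. The documents do not settle how much of the 0.5 is already baseline HbA1c. The 0.20 in step 6 is back-solved and appears in no document.

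Third, Table 4 is weaker evidence than its p-values suggest. Change contains minus baseline, so part of the negative slope is arithmetic. The table gives no sample size, and the pilot in Table 2 included type 1 patients, whom this trial does not enrol.

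Fourth, the covariate list is only what the authors expect, so baseline HbA1c is not barred. True, but listing it as a main effect while it is also an outcome leaves the estimate unchanged (step 2). The structure has to change.

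A reader might also count chance baseline imbalance, or regression to the mean, as a further harm. It is not one. The change-score variance splits as 0.9375 + 0.75² = 1.5 in units of σ², and the second term is the imbalance. It is the same lost precision described again, and regression to the mean acts on both arms alike in expectation.

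**Conclusion.** The point holds as a recommended gain in precision. As written, the primary test is in complete pairs a change-score contrast without adjustment for baseline HbA1c. Adjustment would cut the variance by 37.5% under the plan's single σ and ρ = 0.25 with complete pairs, by 32.5% with the planned attrition, and by about 20–27% if the baseline SD is nearer 1.85. That last SD is an assumption from a small pilot, taken under normality.

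Three stronger readings are not supported:
- *The test is biased or invalid.* It is neither.
- *The trial has 51% power.* That figure gives no credit to any covariate, whereas the plan claims 80% with R² = 0.5.
- *The fix lifts power well above 80%.* Applying the full R² of 0.5 on top of baseline adjustment would give 56 per arm, or 94% power at 89. That could count baseline HbA1c twice, and the documents do not show that it would not.

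**What to change.** In H.2.c, choose one of two equivalent routes (equivalent for complete pairs; close but not identical under dropout):
- Drop the treatment main effect so that both arms share one baseline mean, use an unstructured covariance, and test treatment at 24 weeks. Let the other baseline covariates interact with time; as main effects alone they do not sharpen this contrast in complete pairs.
- Or use ANCOVA of 24-week HbA1c on baseline HbA1c plus the named covariates.

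Under randomisation either route estimates the same treatment effect as the endpoint in H.2.b.

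In H.2.a, replace 4σ²(1−ρ)(1−R²) with 2σ²(1−ρ²)(1−R²). Define R² as the share explained beyond baseline HbA1c, say whether the preliminary value of 0.5 included baseline HbA1c, and state the new value as an assumption with a range. Note that 80% power at 89 per arm needs about 0.20.

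The cost is wording only, with no new data or patients. The change should be made before any outcome comparison by arm is seen.
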